11.5 ELECTRONIC DIARY CARD

Subjects will be required to record the following information each day in a subject e-diary during study participation:

- Confirmation of administration of daily (every 24 hours) dose of RA101495 that includes date, time, and location of injection of RA101495

Subject e-diaries will be collected/dispensed at the time points shown in the Time and Events Table (Table 1). Subjects will be given detailed instructions on how to complete entries in subject diaries throughout study participation.

11.6 EXPLORATORY ASSESSMENTS

11.6.1 QUALITY OF LIFE ASSESSMENTS

Quality of life assessments will be performed according to the Time and Events Table (Table 1). The following QOL questionnaires will be used during this study:

- European Organization for the Research and Treatment of Cancer Quality of Life Questionnaire-C30 (EORTC-QLQ-C30)
- Functional Assessment of Chronic Illness Therapy-Fatigue (FACIT-Fatigue) Scale
- EuroQol-5D (EQ-5D)

11.6.1.1 EORTC-QLQ-C30

The EORTC QLQ-C30 consists of 30 questions, which are incorporated into 5 functional domains (physical, role, cognitive, emotional, and social domains); a global health status/global QOL scale; 3 symptom scales (fatigue, pain, and nausea and vomiting scales); 6 single items that assess additional symptoms (e.g. dyspnea, appetite loss, sleep disturbance, constipation, and diarrhea); and the perceived financial burden of illness treatment [Aronson, 1993; Aronson, 1996]. Subjects answer questions based on symptoms/status over the preceding week.

11.6.1.2 FACIT-FATIGUE

The FACIT-Fatigue Scale is a 13-item, easy to administer tool that measures an individual's level of fatigue during their usual daily activities over the preceding week. The level of fatigue is measured on a five point ordinal scale (4 = not at all fatigued to 0 = very much fatigued) [Webster, 2003].

11.6.1.3 EQ-5D

The EQ-5D is a standardized instrument for measuring generic health status. The EQ-5D consists of the EQ-5D descriptive system and the EQ visual analogue scale (VAS). The EQ-5D descriptive system comprises the following 5 dimensions: mobility, self-care, usual activities, pain/discomfort and anxiety/depression; each dimension has 3 levels: no problems, some problems, extreme problems [EuroQol, 1990]. Subjects answer questions based on symptoms and health status on the day the questionnaire is completed.

11.6.2 TREATMENT SATISFACTION QUESTIONNAIRE

A treatment satisfaction questionnaire using a 5-point Likert response scale will be administered to all subjects to assess overall satisfaction with SC administration of the study medication and to assess their preference for daily SC self-injection at home compared with biweekly infusions given by a health-care professional in the clinic.

The questionnaire will be completed at the end of the 12-week Treatment Period.

11.6.3 BIOMARKERS

Blood samples will be collected at designated time points, concomitant with PK and PD sampling (see [Table 1](#)). All biomarkers will be analyzed by biological or biochemical assays at an accredited laboratory. Detailed instructions regarding sample collection, processing, and shipping will be provided in a separate laboratory manual.

The study of biomarkers related to complement function, thrombosis, inflammation, and liver function will provide further insight in to the clinical efficacy and safety of RA101495 in PNH subjects. Complement protein levels and complement activity will be tested to evaluate response to RA101495 and understand subject characteristics related to variations in response to drug. Markers of thrombosis and inflammation will be tested to assess correlation with complement function and clinical response to RA101495 and to identify markers that may correlate with thrombotic risk in PNH subjects. Additionally, markers for liver function will be assessed to evaluate tolerability of RA101495. A list of analytes will be created through review of the literature, ongoing clinical studies, and ongoing exploratory work and may be finalized after completion of the study.

The completion of these investigations may be conditional based on the results of this or other clinical studies, and samples may be selected for analysis on the basis of clinical outcome. The results of the biomarker investigations may be reported separately from the main clinical study report.

11.6.4 PHARMACOGENOMIC ASSESSMENTS

Participation in the pharmacogenomic assessment is optional and subjects must consent to the pharmacogenomic analysis using a separate consent form.

For subjects who opt to participate in pharmacogenomics studies, a blood sample will be obtained on Day 1. All genomic analyses will be performed at an accredited laboratory. Detailed instructions regarding sample collection, processing, and shipping will be provided in a separate laboratory manual.

Genomic studies will be performed (e.g. deoxyribonucleic acid [DNA] sequencing, DNA copy number analysis, ribonucleic acid [RNA] expression profiling) to explore whether specific genomic features correlate with response or resistance to study drug.

The completion of these investigations may be conditional based on the results of this or other clinical studies, and samples may be selected for analysis on the basis of clinical outcome. The results of the genomic investigations may be reported separately from the main clinical study report.

12 SAFETY REPORTING

12.1 DEFINITIONS

12.1.1 ADVERSE EVENT

An AE is any untoward medical occurrence in a subject administered a pharmaceutical product and which does not necessarily have a causal relationship with this treatment. An AE can therefore be any unfavorable and unintended sign (including a clinically significant abnormal laboratory finding, for example), symptom, or disease temporally associated with the use of a medicinal product, whether or not considered related to the medicinal product.

The following are not considered to be AEs despite requiring hospitalization:

- Pre-existing conditions that, in the opinion of the investigator, did not worsen or progress during study participation
- Routinely scheduled procedures or treatment
- Elective procedures that had been scheduled prior to study participation (i.e. signing of the ICF)

12.1.2 SERIOUS ADVERSE EVENT

An SAE is any untoward medical occurrence that:

- results in death
- is life-threatening (note that this refers to an event in which the subject was at risk of death at the time of the event; it does not refer to an event that hypothetically might have caused death if it were more severe)
- requires hospitalization or prolongation of existing hospitalization
- results in persistent or significant disability/incapacity
- results in a congenital anomaly/birth defect

An SAE may also be any other important medical event that may not be immediately life-threatening or result in death or hospitalization, but may jeopardize the subject or require intervention to prevent one of the other outcomes listed in the definition above. Examples of such events include intensive treatment in an emergency room or at home for bronchospasm, hyperkalemia, or convulsions that do not result in a formal hospitalization.

Elective hospitalizations scheduled prior to study participation (i.e. signing of the ICF) should not be reported as SAEs.

12.1.3 ADVERSE EVENTS OF SPECIAL INTEREST

12.1.3.1 THROMBOTIC ADVERSE EVENTS

All subjects should be monitored for signs and symptoms of thrombotic events at all study visits (weekly for the first 4 weeks followed by every 2 weeks). The method of diagnosis (e.g. ultrasound, computed tomography [CT], magnetic resonance imaging [MRI], venogram, or other [specify]) for any reported event should be recorded in the eCRF. All AEs should be recorded as AEs per [Section 12.1](#) and [Section 12.3](#).

12.1.3.2 HEPATIC ADVERSE EVENTS

All subjects should be monitored for signs and symptoms of hepatic or biliary dysfunction. Liver function tests (LFTs) (ALP, ALT, AST, GGT, Direct Bilirubin and Indirect Bilirubin) are monitored weekly for the first 4 weeks followed by every 2 weeks during the study. The following guideline is provided:

- In subjects with isolated ALT or AST elevation $>2xULN$ with no other explanation for the elevation(s), contact the medical monitor to review the case details and determine if the subject should continue study treatment, reduce dose, or discontinue study treatment. The subject should be monitored until the elevated enzymes return to less than or equal to $2xULN$.
- In subjects with isolated direct bilirubin elevation $>2xULN$ with no other explanation for the elevation(s), contact the medical monitor to review the case details and determine if the subject should continue study treatment, reduce dose, or discontinue study treatment. The subject should be monitored until the direct bilirubin return to less than or equal to $2xULN$.
- Subjects with isolated ALT or AST elevations $>3xULN$ concurrently with direct bilirubin elevation $>2xULN$ and a normal ALP with no other explanation for the elevation should be permanently discontinued. The medical monitor should be contacted as soon as possible to review the case. The subject should be monitored until the elevated enzymes return to Grade 1 National Cancer Institute Common Terminology Criteria for Adverse Events (NCI CTACE Version 4.03) or lower, and the direct bilirubin is less than or equal to $2xULN$.

All AEs should be recorded as AEs per [Section 12.1](#) and [12.3](#).

12.1.3.3 PANCREATIC ENZYME ELEVATIONS

Subjects should be monitored during the study for symptoms of pancreatitis or cholecystitis. Pancreatic enzymes (amylase and lipase) are monitored weekly for the first 4 weeks followed by every 2 weeks during the study.

- In subjects with elevations of amylase or lipase to NCI CTCAE (Version 4.03) Grade 3 ($>2xULN$) study drug should be dose-reduced (if at the 0.3 mg/kg daily dose or permanently discontinued (if at the 0.1 mg/kg daily dose). The subject should be monitored until amylase and /or lipase returns to Grade 1 or lower. The medical monitor should be contacted to review the case.

- In subjects with elevations of amylase or lipase to NCI CTCAE (Version 4.03) Grade 4 (>5xULN) study drug should be permanently discontinued. The subject should be monitored until amylase and /or lipase returns to Grade 1 or lower. The medical monitor should be contacted to review the case

All AEs should be recorded as AEs per [Section 12.1](#) and [Section 12.3](#)

12.1.3.4 INJECTION SITE REACTIONS

The investigator should assess the injection site at each scheduled visit for:

- Pain, tenderness, erythema, and induration severity (Table 5)
- Erythema and induration: record the maximum linear diameter
- Blisters, ulceration, necrosis: record the maximum linear diameter and severity
- Lymphadenopathy

In addition, the investigator will, whenever possible, take de-identified photos of the injection site reaction (ISR).

Injection site reactions should be recorded as AEs per Section 12.1 and Section 12.3, and recorded on the ISR specific eCRF and AE eCRF as appropriate.

Table 5 Grading the Severity of Local Injection Site Reactions

Local Reaction to Injectable Product	Grade 1 (Mild)	Grade 2 (Moderate)	Grade 3 (Severe)	Grade 4 (Potentially Life Threatening)
Pain	Does not interfere with activity	Repeated use of non-narcotic pain reliever >24 hours or interferes with activity	Any use of narcotic pain reliever or prevents daily activity	Emergency room visit or hospitalization
Tenderness	Mild discomfort to touch	Discomfort with movement	Significant discomfort at rest	Emergency room visit or hospitalization
Erythema/redness	2.5 to 5.0 cm	5.1 to 10.0 cm	>10.0 cm	Necrosis or exfoliative dermatitis
Induration/swelling	2.5 to 5.0 cm and does not interfere with activity	5.1 to 10.0 cm or interferes with activity	>10.0 cm or prevents daily activity	Necrosis

12.1.3.5 INFECTION

All subjects should be monitored for signs and symptoms of *Neisseria meningitidis* infection. Subjects are monitored every 2 weeks for adverse events.

To reduce the risk of infection, during the screening period, all subjects must have a negative result for *Neisseria meningitidis* colonization via throat swab prior to study entry. All subjects must have documentation of prior *Neisseria meningitidis* vaccination (and booster if appropriate) prior to study entry.

During the Treatment Period, to mitigate the risk of infection, subjects will be counseled and reminded of early signs and symptoms of *Neisseria meningitidis* infection. A patient safety card detailing the signs and symptoms of infection with instructions to seek immediate medical attention will be provided to each subject. The card will also describe the subject's participation in the study and the risks of infection associated with inhibition of the terminal complement system. The patient safety card must be carried with the patient at all times while on treatment.

All AEs should be recorded as AEs per [Section 12.1](#) and [Section 12.3](#)

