RA10495 administered for 7-days achieved inhibition of hemolysis that was rapid and sustained at $\geq 95\%$ across the dosing period in all subjects, (Figure 6). The mean percent inhibition of hemolysis compared to baseline reached $>95\%$ beginning at the first time point, 3 hours after dosing on Day 1, and continued throughout 7 days of dosing; all individual subjects showed $\geq 90\%$ inhibition of hemolysis at all time points. At 24 hours after the last dose, inhibition of hemolysis was observed to be $\geq 97\%$ in all subjects. Eight days after the last dose of RA10495, the mean inhibition of hemolysis remained $\geq 56\%$. Two subjects had inhibition of hemolysis $>70\%$ through 8 days after the last day of dosing. Hemolysis returned to pre-dose levels in all subjects within two weeks following the last dose.

Figure 5 Mean (SD) Red Blood Cell Lysis Over Time by Dose Group Following Single-Dose SC Administration in Healthy Volunteers (Study RA101495-1001)

[figure not shown]
[figure not shown]

Figure 6 Mean (SD) Red Blood Cell Lysis Over Time by Dose Group in the Multiple-Dose Cohort Once Daily for 7-Days in Healthy Volunteers in (Study RA101495-1001)

Note: Figure on the right is a duplicate of the figure on the left with an expanded y-axis.

Safety: Across all the SAD cohorts, 7 of the 14 of the subjects treated with RA101495, had adverse events (AEs), which occurred more frequently in the highest dose cohort (0.4 mg/kg). All subjects in the MD (0.2 mg/kg) had at least 1 AE. All AEs resolved. In all cohorts of the SAD and MD, there were no AEs that led to study drug discontinuation. No serious AEs (SAE) or deaths occurred during the study.

In the SAD the most common AEs regardless of causality in subjects who received single-doses of RA101495 were injection site erythema (3 subjects, cohort 4), upper respiratory tract infection (URI) (1 subject, cohort 1; 2 subjects, cohort 4), and headache (2 subjects, cohort 4). Other AEs that occurred in 1 subject each were bronchitis (cohort 1); catheter site phlebitis (cohort 3); fatigue (cohort 4); and back pain (cohort 4). AEs in subjects who received placebo were diarrhea, myalgia, headache, and rash, all in 1 subject each.

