All subjects will receive treatment with RA101495 from Day 1 to Day 84 during the Treatment Period. Subjects completing the 12-week Visit and are demonstrating benefit, in consultation with the treating physician, will have the option to enroll in a long-term open-label extension study to continue receiving treatment with RA101495. If a subject chooses not to participate in the extension study, the subject will receive standard-of-care treatment off-study as recommended by the treating physician.

8.3 **SUBJECT REGISTRATION PROCEDURES**

8.3.1 **SCREENING AND ENROLLMENT**

Written informed consent must be obtained before ANY study-related procedures are performed.

At the Screening Visit, subjects will be assigned a unique subject number. The following assessments will be performed during screening.

- Demographic and baseline characteristics
- Medical history, including a detailed history of PNH diagnosis information, symptoms, complications, and treatment over the 6 months prior to Screening
- Review and documentation of prior (within the previous 30 days) and concomitant medications
- Physical examination, including height and weight
- Vital signs (heart rate, body temperature, blood pressure) in the sitting position after resting for at least 5 minutes
- 12-lead ECG in a supine position (lying down) for at least 5 minutes prior to, and during, the recording
- Blood samples for clinical chemistry (including LDH), hematology, and coagulation
- Urine sample for urinalysis
- Serum pregnancy for females of childbearing potential only
- Throat swab for *Neisseria meningitidis*

The inclusion and exclusion criteria will be reviewed to determine subject eligibility for study participation at the Screening Visit and prior to drug dosing on Day 1.

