9 SELECTION OF STUDY POPULATION

9.1 INCLUSION CRITERIA

To be eligible for this study, subjects must meet **ALL** of the following inclusion criteria:

1. Male or female ≥ 18 years
2. Completed informed consent procedures, including signing and dating the informed consent form (ICF).
3. Diagnosis of PNH by flow cytometry
4. Inadequate response to eculizumab defined as having received eculizumab for at least 6 months plus one or more of the following criteria:
 - A documented lactate dehydrogenase (LDH) level ≥ 1.5 x the ULN within 90 days prior to Screening
 - Presence of a known C5 mutation conferring resistance to eculizumab
5. Female subjects of child bearing potential must have a negative pregnancy test at Screening and within 24-hours prior to the first dose of RA101495
6. Sexually- active female subjects of child-bearing potential (i.e. women who are not post-menopausal or who have not had a bilateral oophorectomy, hysterectomy, or tubal ligation) and all male subjects (who have not been surgically sterilized by vasectomy) must agree to use effective contraception during the study. Effective contraception is defined as:
 - Hormonal contraception (e.g. oral contraceptive, transdermal contraceptive, contraceptive implant, or injectable hormonal contraceptive) for at least 3 months prior to study drug administration, throughout the study, and for 4 weeks after the last dose of study drug.
 - Double-barrier birth control (e.g. male condom, female condom, diaphragm sponge, or cervical cap together with spermicidal foam/gel/film/suppository) starting at the Screening Visit, throughout the study, and for 4 weeks after the last dose of study drug.
 - Intrauterine contraception/device starting at the Screening Visit, throughout the study, and for 4 weeks after the last dose of study drug.
 - Total abstinence from sexual intercourse for at least one complete menstrual cycle prior to the Screening Visit, throughout the study, and for 4 weeks after the last dose of study drug
 - Maintenance of a monogamous relationship with a male partner who has been surgically sterilized by vasectomy.

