12.3.1.2 SERIOUS ADVERSE EVENTS

Any SAE experienced by the subject from signing the ICF through to 30 days after the last dose of study drug, regardless of severity or causality, must be recorded on the eCRF and SAE Form.

The study site must formally notify the Sponsor of the SAE within 24 hours from the time the study site becomes aware of the SAE. A formal notification must be submitted to the Sponsor regardless of the following:

- severity
- causality

- whether or not the subject received study treatment or underwent study related procedures

The IEC/IRB will be notified as required by local regulations. The investigator will be responsible for submitting the required safety information to the appropriate IEC/IRB, including any safety reports received from the Sponsor as well as any SAEs occurring at his or her site.

The Sponsor, or designee, will prepare any required safety reports for regulatory authorities and all active investigators. These reports will be provided as addenda to the Investigator's Brochure, and the investigator will place these with the brochure.

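### The meningococcal safety card and counselling stop with treatment, although the protocol's own data show complement inhibition lasting up to two weeks after the last dose

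*Protocol*

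**What the plan says.** Three places in the protocol (synopsis, 8.1 and 12.1.3.5) set the same duty: "The patient safety card must be carried with the patient at all times while on treatment". Counselling has a matching limit: "During the Treatment Period, to mitigate the risk of infection, subjects will be counseled and reminded of early signs and symptoms of" *Neisseria meningitidis* infection. Section 8.2.2 fixes that period: "All subjects will receive treatment with RA101495 from Day 1 to Day 84 during the Treatment Period".

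Nothing in the protocol or SAP extends either instruction beyond the last dose. The End-of-Study procedures in section 8.4.1 contain no infection reminder, and no visit is scheduled after treatment ends.

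Two other provisions do run past the last dose. For most of the listed contraceptive methods, section 9.1 requires use "throughout the study, and for 4 weeks after the last dose of study drug". Section 12.3.1.2 requires SAE recording "through to 30 days after the last dose of study drug".

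**The concern.** By the protocol's own account, the card tells subjects and outside clinicians about the infection risk that comes with blocking terminal complement. It is needed for as long as the block lasts, which is not the same as the dosing period. Section 6.3 shows the block fading over one to two weeks.

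Some subjects will pass through that window off drug:

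- Early withdrawals cannot enter the extension (section 8.1).
- At 0.1 mg/kg, Grade 3 amylase or lipase elevations, and any Grade 3 or higher event outside the hepatic and pancreatic rules, require permanent discontinuation (sections 12.1.3.3 and 12.1.3.6).
- The extension is open only to completers who are benefiting. A subject escalated to 0.3 mg/kg who still does not benefit leaves after the highest exposure in the trial.

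Table 1 lists RA101495 administration at the Day 84 visit, so a completer may leave the last scheduled contact freshly dosed. If that subject puts the card away, a fever in the next two weeks may not prompt urgent care, and a treating physician may not learn of the C5 inhibitor. The SAE window would record the infection but would not get it treated sooner.

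**Working it through.** **Inputs**

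- Multiple-dose Phase 1 cohort, 0.2 mg/kg daily for 7 days, four subjects on active drug (section 6.3): Kel 0.0043 per hour and half-life 161.9 h. The single-dose half-lives ranged from 155.6 to 185.4 h.
- Offset in that cohort (section 6.3): at least 97% inhibition in all subjects 24 hours after the last dose. Then "Eight days after the last dose of RA10495, the mean inhibition of hemolysis remained" at or above 56%; two subjects were above 70% through day 8. Finally, "Hemolysis returned to pre-dose levels in all subjects within two weeks following the last dose".
- AUC0-24 in h·µg/mL (Table 2): 151.3 observed on Day 7 of 0.2 mg/kg; 141.5 predicted at steady state for 0.10 mg/kg; 152.8 predicted for 0.14 mg/kg, the top of the weight-bracket range.
- No exposure is given for 0.3 mg/kg daily.

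**1. Reproduce the half-life.** ln 2 / Kel = 0.6931 / 0.0043 = 161.2 h, against 161.9 h stated. The difference is rounding of Kel.

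**2. Drug remaining after the last dose.** Fraction = 0.5^(hours / 161.9).

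| Day after last dose | Fraction remaining |
|---|---|
| 8 | 0.5^(192/161.9) = 44% |
| 14 | 0.5^(336/161.9) = 24% |
| 30 | 0.5^(720/161.9) = 4.6% |

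This fits the reported partial inhibition at day 8 and recovery by two weeks.

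**3. Offset at 0.1 mg/kg daily.** If effect follows concentration and the half-life is constant, the shift relative to Phase 1 is log2(AUC ratio) × 161.9/24 days.

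- 0.10 mg/kg: log2(141.5/151.3) × 6.75 = −0.7 day.
- 0.14 mg/kg: log2(152.8/151.3) × 6.75 = +0.1 day.

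The Phase 1 offset of up to about 14 days is therefore a fair guide.

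**4. Offset at 0.3 mg/kg daily (assumed range).** Three scalings from the 0.1 mg/kg prediction:

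| Scaling | AUC0-24 at 0.3 mg/kg | Shift | Recovery by, at most |
|---|---|---|---|
| Table 2 trend: exponent ln(152.8/141.5)/ln 1.4 = 0.228 | 141.5 × 3^0.228 = 181.8 | 1.8 days | 14 + 1.8 = 15.8 days |
| Phase 1 single doses: AUC0-24 of 21,440 to 112,300 over an 8-fold dose range, exponent 0.80 | 141.5 × 3^0.80 ≈ 340 | 7.9 days | 14 + 7.9 = 21.9 days |
| Linear | 3 × 141.5 = 424.5 | 10.0 days | 14 + 10.0 = 24.0 days |

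Using Cmax instead (7.29 µg/mL in Phase 1, 6.57 predicted at 0.1 mg/kg) gives 1.5 days with the Table 2 trend and 9.7 days with linear scaling.

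**5. Is 30 days enough?** In the linear case, exposure starts at 424.5/151.3 = 2.81 times the Phase 1 level. After 30 days it is 2.81 × 4.6% = 13% of the Phase 1 Day 7 level. That is below the 24% left at day 14 in Phase 1, by which time hemolysis had recovered. With the longest reported half-life, 185.4 h, the linear shift is log2(2.81) × 7.73 = 11.5 days, giving 25.5 days. All cases fall inside the existing SAE window.

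**The case against.** The protocol sets a minimum carrying duty and never tells subjects to discard the card. The card is not among the items returned under section 8.4.1, and its own text is not in the documents. This stands: the claim is that the protocol sets too short a duration, not that every subject will be unprotected.

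Subjects who leave the study go on to standard of care under their physician. All have had at least six months of eculizumab, documented vaccination, a negative throat swab and counselling in the trial. This lowers the likely harm. It does not cover the gap, because the protocol gives no post-dose instruction on RA101495 for the subject to follow or show to another clinician.

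The Day 84 visit falls inside the Treatment Period, so a reminder there is already permissible. It is, but it is not listed, and section 8.4.1 has no equivalent for early stops.

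Stopping directly from 0.3 mg/kg is uncommon, because most Grade 3 or higher events at that dose lead to dose reduction first. Linear scaling also sits above the protocol's less-than-proportional single-dose data. Both points are fair. They make the 24-day end of the range less likely and leave the 14-day figure at 0.1 mg/kg unchanged.

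The offset data come from an ex-vivo sheep red cell assay in four healthy volunteers. Two weeks is an upper limit, and no meningococcal risk is attached to partial inhibition. That limits precision, but these are the data the sponsor has, and they argue against assuming that the risk ends with the last dose.

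**Conclusion.** The concern holds. Carrying the card and counselling end with treatment, while the effect that makes them necessary persists. The uncovered time is up to about 14 days at 0.1 mg/kg daily. For subjects who finish or stop at 0.3 mg/kg daily it is up to about 16 to 24 days.

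The first figure rests on the Phase 1 offset carrying over to PNH subjects with similar exposure. The second also assumes a constant half-life, an effect that follows concentration, and a dose scaling that the protocol does not provide.

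Few subjects are affected: enrolment is at most 8, and those who enter the extension stay on drug. No endpoint, sample size or analysis changes. The reason to act is subject safety, at very low cost.

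**What to change.** In the synopsis, section 8.1 and section 12.1.3.5, state that the card is carried, and the symptom instructions apply, during treatment and for 30 days after the last dose. This matches the SAE window in section 12.3.1.2. Put the same period on the card. Add a documented infection reminder to the Day 84 visit and to the End-of-Study procedures in section 8.4.1, so that early stops are covered too.

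The cost is a wording change in three places and on the card, plus a short reminder at a visit already held. No visit, test or analysis is added. The downside is that subjects carry the card for about a month longer.
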